7. STUDY DEVICE

7.1. Study Device

The Mastoid oscillator is a small device (9 x 6 x 3 cm, ~200g see Appendix 1 for images) custom-made for the PI by Bridgekey Engineering Solutions of Rochester NY. It is secured with a Velcro elastic headband over the mastoid in the post-auricular region of the Ménière's affected ear. The contoured surfaces of the device ensure a smooth fit against the head and also no displacement of the ear. The placebo oscillator replicates the sound of the Mastoid oscillator but without the vibration to the skull. The device runs on a rechargeable battery and there is an on/off button. The start of vibration or sound is delayed by a few seconds after the device is turned on.

Between subject uses the device is cleaned with an alcohol wipe and stored by the study Research Technician in the Clinical Trials office of the ENT department at the Clinton Woods office, within a locked cabinet.

Note that this study is not intended to determine safety or effectiveness for commercial distribution of the oscillator or placebo oscillator. These are custom devices that are ordered by the principal investigator and are not generally available to other physicians. They are not generally available in finished form for purchase or for dispensing upon prescription and are not offered for commercial distribution through labeling or advertising. They are intended to meet the special needs of the principal investigator in the course of his professional practice.

7.2. Subject Enrollment/Randomization

Subjects will be randomized to either oscillation or placebo. The method for assigning study group will be a look-up table that is held in secret for the study personnel by the Chair of the Department of Otolaryngology, who will release either 'Device A' or 'Device B' at time of randomization from a pre-determined table with 1:1 group ratio.

8. RISK/BENEFIT ASSESSMENT

8.1. Potential Risks

- 1) Physical discomfort: Soreness at the site of oscillation. There is a theoretical risk of worsening of the symptoms of dizziness, however worsening of symptoms never occurred in any of the 66 patients involved in the pilot study. In addition, the vibration of the skull routinely occurs with drilling on the mastoid, something that is performed frequently on patients with middle ear and mastoid disease throughout the world. No complications directly related to the vibration of drilling have ever been reported.
- 2) Invasion of subject privacy.

8.2. Protection Against Risks

The risks of discomfort will be minimized by having the oscillation procedure performed by trained personnel/otolaryngologists in a professional office setting.

Privacy will be protected by minimizing the number of people with access to the subject's identifying data, which will be stored in REDCap, making use of its built in privacy protections. All study personnel will have training in human subjects protections.

8.3. Potential Benefits to Subjects

There is no benefit to subjects of participating.

8.4. Alternatives to Participation

The alternatives to participation in the study include traditional, time-honored invasive treatments for Ménière's disease.

9. CONFIDENTIALITY OF DATA AND INFORMATION STORAGE

Information about study subjects will be kept confidential and managed according to the requirements of the Health Insurance Portability and Accountability Act of 1996 (HIPAA). Those regulations require a signed subject authorization informing the subject of the following:

- What protected health information (PHI) will be collected from the subjects in this study
- Who will have access to that information and why
- Who will use or disclose that information
- The rights of a research subject to revoke their authorization for the use of their PHI

In the event that a subject revokes authorization to collect or use PHI, the investigator, by regulation, retains the ability to use all information collected prior to the revocation of subject authorization. For subjects that have revoked authorization to collect or use PHI, attempts should be made to obtain permission to collect

at least vital status (i.e. that the subject is alive) at the end of their scheduled study period. We will exercise the following practices to maintain confidentiality of data and protecting against unauthorized disclosure:

- not downloading identifying information from REDCap except subject ID number (i.e., keep any identifying information separately from any research data)
- locking up research files while they are unsupervised
- using screensavers
- shredding excess copies of paper documents
- protections for codes that link patients to their data
- electronic and physical security of data storage devices and networks
- security measures to protect storage and transmission of electronic data

10. RESEARCH INFORMATION IN MEDICAL RECORDS

Study participation will be indicated in the medical record.

11. DATA ANALYSIS AND MONITORING

11.1. Sample Size Determination

The pilot study^{2,3} showed that mastoid oscillation treatment was highly efficacious. Of 66 subjects that were treated, 22 (33.3%) achieved complete control, 30 (45.4%) achieved substantial control, 11 (16.7%) achieved limited control and three (4.5%) had insignificant control. A control group (N=30) with delayed start of treatment had just 2 subjects with improvement of symptoms (complete or substantial) during the wait period (6.6%).

For our sample size projection, we assume that the Mastoid Oscillation arm will have a 75% rate of achieving substantial or complete control, and 12% for the placebo group. With 15 subjects in each group, using Fisher's Exact test, the design has 95% statistical power with alpha of 0.012.

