1.2. Background

Since Hallpike and Cairns first described the histologic findings of the inner ear in Ménière's disease in 1938, attention has focused on the cause for these findings. Despite reconfirmation of the histologic findings over the years, such that endolymphatic hydrops is universally accepted as synonymous with Ménière's disease, the etiology for these findings and the clinical symptoms remains elusive.

Paralleling the futile search for the cause, there has been a rich and equally frustrating history regarding the treatment of Ménière's disease. The history and literature is replete with conservative measures attempting to control symptoms without being destructive, as well as more predictable but destructive procedures for recalcitrant symptoms.

One of the more lively and ongoing debates centers around the role and the mechanism of action of endolymphatic shunt/decompression procedures. Those who espouse endolymphatic sac surgeries believe in their value and effect. Naysayers cite the natural history of the disease and the results of the foreshortened sham surgery study completed in Denmark.¹ Even proponents of endolymphatic sac surgery can't agree on the management of the sac, some shunting into the cerebrospinal fluid space, some shunting into the mastoid, some suggesting that fluid pressures can be controlled with valves and others avoiding shunting completely and merely decompressing the sacs. Interestingly, aside from mild variations, all approaches seem to produce similar results. Although foreshortened and resulting in inadequate numbers for statistical analysis, even the sham study¹ seemed to produce similar results. Is there any unifying hypothesis that would explain these observations?

Those who perform endolymphatic sac surgeries believe there is a temporal relationship between the surgical procedure and the improvement in symptoms that the patient experiences. However, the reason for the improvement is unknown. It is merely conjecture that the effect of the endolymphatic shunt is decompressive drainage through the endolymphatic duct and sac. This has never been scientifically demonstrated. In fact, the observation that decompression of the endolymphatic sac without shunting is equally effective would suggest that decompressive drainage may not be the reason that endolymphatic sac procedures work.

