2.2. Rationale for Study Design

The pilot study has already determined that approximately 75% of patients undergoing mastoid oscillation for Ménière's disease refractory to medical treatment significantly improve or resolve their symptoms, compared with less than 10% in a 'waiting list' control group. This means that 75% of patients seen who here-to-fore would have had surgery or a destructive procedure offered now have a non-surgical/non-destructive option available. The ongoing debate that blocks use of this treatment routinely in treatment of patients with refractory Ménière's disease is whether this improvement is better than the natural history of the disease. Therefore, objections demand a control group/study before this form of treatment is accepted as a viable alternative before considering surgical or ablative approaches to the management of Ménière's disease refractory to medical treatment. We have now designed and will have produced a null device (control) which should address this objection/concern. This device will produce the sound of oscillation, but there will be no oscillation delivered. Therefore, the control/null device will be identical to the mastoid oscillator, except that there will be no oscillation whatsoever delivered.

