6. SUBJECT WITHDRAWALS

Subjects will be advised in the written informed consent forms that they have the right to withdraw from the study at any time without prejudice. Subjects will be withdrawn from the research without their consent by the investigator if they are non-compliant (miss scheduled study visits), or if the investigator determines that it is in the best interest of the subject. Also if the subject develops bilateral Ménière's disease during the study they will be withdrawn. There are no additional study activities requiring completion prior to subject withdrawal from the study. Subjects withdrawn from the study will not be replaced.

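### Section 11.1 states 95% power, but its own inputs give about 83% (two-sided) or 87% (one-sided), and the 12% placebo rate behind it has no stated source

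*Combined protocol and SAP*

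**What the plan says.** Section 11.1 of the combined protocol and SAP gives one scenario: "we assume that the Mastoid Oscillation arm will have a 75% rate of achieving substantial or complete control, and 12% for the placebo group". For Fisher's exact test at alpha 0.012 and 15 per arm, it states 95% power. It does not say whether the test is one- or two-sided, or why alpha is 0.012.

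The pilot data in the same section are, for treated patients, "Of 66 subjects that were treated, 22 (33.3%) achieved complete control, 30 (45.4%) achieved substantial control", and for controls, "A control group (N=30) with delayed start of treatment had just 2 subjects with improvement of symptoms". Section 2.2 describes those controls as a waiting list ("compared with less than 10% in a 'waiting list' control group"). The step from 6.6% on the waiting list to 12% on placebo is not explained.

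Section 2.1 gives this trial's control arm a device that makes the same sound without vibration. Section 3.1 allows as many as 40 enrolled to obtain 15 randomised to each arm. Section 6 removes subjects who miss visits and adds: "Subjects withdrawn from the study will not be replaced". Section 11.2 plans a chi-square or Fisher test on the vertigo classes and names no effect estimate or interval for the primary outcome.

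**The concern.** Every input to the power calculation is printed except the sidedness, so the 95% can be checked directly. If it does not follow, the plan understates the chance of missing the effect it assumes: 5% as stated, against 17% (two-sided) or 13% (one-sided) as computed.

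The placebo rate matters for a related reason. With 15 per arm, power falls steeply as the control rate rises, and the plan shows only one control rate. The data behind that rate come from people who received no device, whereas the control arm here has four positioned, monitored 30-minute sessions with a sounding device. A reader cannot see from section 11.1 how much the power depends on this assumption, or on keeping all 15 per arm.

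**Working it through.** **Inputs.** Response (complete or substantial control) 75% and 12%; 15 per arm; Fisher's exact test; alpha 0.012 (all section 11.1). Pilot waiting list 2/30 (section 11.1). Responses are taken as independent binomials.

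**Step 1: reproduce the stated 95%.** Power is the sum, over every pair of responder counts (i active, j placebo) with Fisher p at or below alpha, of Bin(i; 15, 0.75) × Bin(j; 15, 0.12). For the two-sided test at 0.012, each placebo count needs a minimum active count:

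| Placebo responders j | P(j) at 12% | Active needed | P(at least that many) at 75% | Product |
|---|---|---|---|---|
| 0 | 0.1470 | 7 | 0.9958 | 0.1464 |
| 1 | 0.3006 | 9 | 0.9434 | 0.2836 |
| 2 | 0.2870 | 10 | 0.8516 | 0.2444 |
| 3 | 0.1696 | 11 | 0.6865 | 0.1164 |
| 4 | 0.0694 | 12 | 0.4613 | 0.0320 |
| 5 | 0.0208 | 13 | 0.2361 | 0.0049 |
| 6 | 0.0047 | 14 | 0.0802 | 0.0004 |

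The products add to 0.828; higher placebo counts contribute almost nothing. Two-sided power at 0.012 is **82.8%**. The same enumeration gives 86.8% one-sided at 0.012, 92.0% two-sided at 0.05 and 96.5% one-sided at 0.05.

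**Step 2: look for a route to 95%.** Each near match departs from the printed inputs:
- 20 per arm, two-sided at 0.012: 95.0%. This would mean analysing all 40.
- The observed pilot rates, (22 + 30)/66 = 78.8% against 2/30 = 6.7%, two-sided at 0.012: 95.7%.
- A one-sided normal approximation at 0.012: 94.3%, which is not Fisher's test.
- One-sided Fisher at 0.05: 96.5%.

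Nor is 0.012 the attained size of a nominal 0.05 Fisher test at a common 12% rate; that is 0.0084 two-sided and 0.0158 one-sided. The documents do not show which route, if any, was taken.

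**Step 3: what the pilot controls can support.** The exact (Clopper-Pearson) 95% interval for 2/30 runs from the 2.5% point of Beta(2, 29) to the 97.5% point of Beta(3, 28), which is 0.8% to 22.1%. The planning value of 12% lies inside it, and so does a rate nearly twice as high. This interval describes untreated patients, not sham patients.

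**Step 4: sensitivity.** Two-sided Fisher, active 75%. Control rates other than 12% are assumptions, because the documents give no rate for a sham device.

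| Control rate | Evaluable per arm | Power, alpha 0.012 | Power, alpha 0.05 |
|---|---|---|---|
| 12% | 15 | 82.8% | 92.0% |
| 20% | 15 | 64.2% | 78.5% |
| 22% | 15 | 59.2% | 74.3% |
| 30% | 15 | 39.1% | 55.6% |
| 12% | 13 | 70.9% | 91.2% |

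**The case against.** The best defence of the plan has four parts.

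- **The 12% is already cautious.** It is nearly double the 6.6% seen on the waiting list, so it was not simply copied from untreated patients. This stands. What remains is that no reason is given for 12%, and no sham data are cited.
- **Enrolment has a margin.** As many as 40 may be enrolled for 30, and 30/(1 − 0.25) = 40. This stands in part: it would be wrong to say that loss was ignored. But section 3.1 ties the margin to reaching 15 randomised per arm, and section 6 rules out replacement, so loss after randomisation appears uncovered.
- **Loss costs little at a conventional alpha.** At two-sided 0.05, going from 15 to 13 per arm moves power only from 92.0% to 91.2%. This stands. The larger fall, to 71%, occurs at the stated 0.012.
- **A multi-scenario table is good practice, not correction of an error.** True, which is why the sensitivity points are secondary. The 95% itself is a figure that does not follow from its inputs.

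A reader might also infer from section 1.2, where even the sham surgery study "seemed to produce similar results", that the sham response here must be high. The documents do not support this. The same sentence says that study was cut short with too few patients for analysis, and it gives no rate. Section 1.2 goes on to note that the sham also used the mastoid drill, which the protocol suspects is the active element. That sham may resemble oscillation more than it resembles a device without vibration.

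**Conclusion.** The 95% in section 11.1 is wrong as written. Its own inputs give 82.8% two-sided or 86.8% one-sided, a shortfall of about 12 or 8 percentage points. This rests only on independent binomial responses. It does not depend on doubting the 12% or on any dropout, so a reader who attributes the shortfall to the waiting-list data or to withdrawals would have the cause wrong.

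The lack of a basis for 12%, and of any allowance for loss after randomisation, are real gaps, but they support sensitivity analysis only. A reader might conclude that the trial is more likely to miss a true 75% response than to find it. Two-sided power drops below one half only when the sham rate is just above 25% (alpha 0.012) or just above 32% (alpha 0.05), and no figure in the documents supports rates that high. Even at 22%, about the upper limit for untreated patients, power is 59% or 74%. Nor do the documents say that a non-significant result would be read as proof of no effect.

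**What to change.** **Section 11.1**
- State whether the test is one- or two-sided, and state the intended alpha with its reason.
- Replace 95% with the matching figure: about 83% (two-sided, 0.012), 87% (one-sided, 0.012) or 92% (two-sided, 0.05).
- Add a short table of power over assumed sham rates and 13 to 15 evaluable subjects per arm, labelled as assumptions.
- State that the cited control data come from an untreated waiting list, and that no sham-device data support 12%. Do not add a derivation for 12% unless one exists.

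**Section 3.1**
- Say whether the margin up to 40 covers losses after randomisation or only before it, consistently with the no-replacement rule in section 6.

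**Section 11.2**
- Report the risk difference for complete or substantial control, the outcome on which power was computed, with an exact 95% CI.

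These are wording changes. No extra patients are needed. The cost is a less favourable stated power.

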2. STUDY DESIGN

2.1. Overview

This is a single center, randomized, placebo-controlled trial of mastoid oscillation for treatment of Ménière's disease. Eligible subjects will be randomized using a 1:1 allocation to either mastoid oscillation or placebo (oscillator device that provides the same sound but no vibration of the mastoid) received for 30 minutes at four weekly study visits, with efficacy determination via change in frequency and severity of Ménière's symptoms following the final study visit.

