3. CHARACTERISTICS OF THE RESEARCH POPULATION

3.1. Subject Characteristics

- a) **Number of Subjects:** We plan to enroll up to 40 subjects in order to accrue 15 randomized to the treatment arm of the study and 15 assigned to the placebo/control arm.
- b) **Gender and Age of Subjects:** Subjects 18 years of age and older will be included in the study and there will be no restriction on gender.
- c) **Racial and Ethnic Origin:** There will be no restriction based on race or ethnicity.

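### The stated 95% power at alpha 0.012 does not follow from the plan's own inputs: Fisher's exact test with 15 per arm gives about 83% two-sided (87% one-sided)

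*Combined protocol and SAP*

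**What the plan says.** Section 11.1 takes its rates as follows: "we assume that the Mastoid Oscillation arm will have a 75% rate of achieving substantial or complete control, and 12% for the placebo group". The power statement comes next: "With 15 subjects in each group, using Fisher's Exact test, the design has 95% statistical power with alpha of 0.012". Section 2.1 confirms equal allocation. Section 3.1 sets the enrolment ceiling: "We plan to enroll up to 40 subjects in order to accrue 15 randomized to the treatment arm", with the same number in the placebo arm.

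The plan does not say whether the test is one- or two-sided, or whether 0.012 is the nominal level or the size actually attained. Section 11.2 names the chi-square or Fisher's exact test for the primary comparison across classes A to F, and gives neither an alpha nor a sidedness.

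**The concern.** The rates, group size, test and alpha are all given, so the power can be computed exactly and should come out at 95% for at least one choice of sidedness. Fisher's exact test is conservative in samples this small, and a large-sample formula tends to flatter it, so the figure deserved checking.

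This sentence is the plan's only quantitative justification for 15 per arm. The trial was set up to answer the objection that the pilot lacked controls (Sections 1.2 and 2.2). If it finds no difference, readers will weigh that result against the stated power. They would take the risk of missing the assumed effect to be 1 in 20 when, at the stated alpha, it is about 1 in 6 (two-sided) or 1 in 8 (one-sided).

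**Working it through.** **Inputs (Sections 11.1 and 2.1).** Response probabilities 0.75 and 0.12; 15 per arm, 1:1; Fisher's exact test; alpha 0.012; stated power 95%.

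**Formula.** With *i* responders on oscillation and *j* on placebo,

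Power = Σᵢ Σⱼ Bin(*i*; 15, 0.75) × Bin(*j*; 15, 0.12) × 1[Fisher p(*i*, *j*) ≤ 0.012],

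summed over all 16 × 16 outcomes.

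**Two-sided, worked by placebo count.** For each *j*, find the smallest *i* that reaches p ≤ 0.012, then multiply the probability of *j* by the probability of at least that *i*.

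| *j* | P(*j*) | Smallest *i* | P(at least that *i*) | Product |
|---|---|---|---|---|
| 0 | 0.1470 | 7 | 0.9958 | 0.1464 |
| 1 | 0.3006 | 9 | 0.9434 | 0.2836 |
| 2 | 0.2870 | 10 | 0.8516 | 0.2444 |
| 3 | 0.1696 | 11 | 0.6865 | 0.1164 |
| 4 | 0.0694 | 12 | 0.4613 | 0.0320 |
| 5 | 0.0208 | 13 | 0.2361 | 0.0049 |
| 6 | 0.0047 | 14 | 0.0802 | 0.0004 |

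The products sum to 0.8281; larger *j* add nothing at this precision. A simulation of 400,000 trials gave 0.8283.

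**One-sided.** The same sum gives 0.8675 (simulation 0.8676).

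**Type II error.** Two-sided: 1 − 0.828 = 0.172, and 0.172 / 0.05 = 3.4. One-sided: 1 − 0.8675 = 0.1325, and 0.1325 / 0.05 = 2.6.

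**Could 0.012 be an attained size?** For Fisher's test at conventional nominal levels:

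| Nominal level | Power | Size at a common 12% rate | Maximum size |
|---|---|---|---|
| Two-sided 0.05 | 92.0% | 0.0084 | 0.0177 |
| One-sided 0.05 | 96.5% | 0.0158 | 0.0216 |
| Two-sided 0.025 | 86.8% | 0.0018 | about 0.009 |

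None gives 95% together with 0.012.

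**Could another formula have been used?** At alpha 0.012:

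- pooled z: 89.5% two-sided, 94.3% one-sided;
- arcsine: 90.1% two-sided, 93.8% one-sided;
- unpooled z: 97.7% two-sided, 98.8% one-sided;
- uncorrected chi-square, exact power: 91.6%.

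The one-sided approximations come close to 95%, but none of these is the test that the sentence names.

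**What would make the pair true for Fisher's test?**

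- Two-sided: 20 per arm gives 94.98% and 21 gives 95.3%.
- One-sided: 18 per arm gives 94.8% and 19 gives 96.6%.
- With 15 per arm: a placebo rate of about 4.5% or less (two-sided) or 7% or less (one-sided).
- The observed pilot rates (52/66 = 78.8% and 2/30 = 6.7%) give about 96% two-sided, but Section 11.1 assumes different rates.

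**Sensitivity to the placebo rate (assumed values).** At two-sided 0.012, power falls to 64% with a 20% placebo response and to 39% with 30%.

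**The case against.** Nobody disputes the arithmetic at alpha 0.012. The case on the other side concerns how far it reaches.

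- **Sidedness.** The plan gives none, so the more-than-threefold type II error holds only for a two-sided test. This stands; one-sided it is 2.6 times. The 95% is wrong either way.
- **A mislabelled attained size.** One-sided Fisher at nominal 0.05 does exceed 95% power, and its size is 0.0122 if both arms respond at 10%. So a labelling slip is possible. But 10% is not a rate that the plan uses, at 12% the size is 0.0158, and the text does not present 0.012 in this way.
- **Consequence.** Every Fisher reading from 0.012 to 0.05 gives between 82.8% and 96.5% power, above a conventional 80%. Fifteen per arm remains defensible if 12% holds. This stands, and it is why the remedy is wording rather than more patients.
- **Using the 40-subject ceiling for 20 per arm.** This stands as a caution. The ceiling leaves a margin of 40 − 30 = 10, and Section 6 says withdrawn subjects are not replaced. Twenty analysed per arm would need every enrolled subject to be randomised and retained.
- **Match to the analysis.** Section 11.2 compares classes A to F, whereas the power rests on a two-category split that appears only in 11.1. This stands and belongs in the fix.

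**Conclusion.** The concern holds. On the plan's own inputs, power at alpha 0.012 is 82.8% two-sided or 86.8% one-sided, a shortfall of 12.2 or 8.2 percentage points from the stated 95%. No conventional nominal level for Fisher's test, in either direction, yields both stated figures at the stated rates.

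This rests on the assumed 75% and 12% rates, exactly 15 analysed per arm, and a primary comparison of complete or substantial control against everything else. Any loss of subjects, or a placebo response above 12%, lowers the power further. The only supporting figure for the placebo rate is 2 of 30 in an untreated waiting-list group. The error does not invalidate the design. It does make the sole justification for the sample size materially wrong, and the threshold it depends on is never carried into the analysis.

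**What to change.** Make these changes before the blind is broken.

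1. **Section 11.1.** State the sidedness and the nominal alpha, and replace the power figure with the exact one: 83% at two-sided 0.012, 87% at one-sided 0.012, or 92% at two-sided 0.05, whichever threshold the investigators intend. If 0.012 was meant as an attained size, say so and give the nominal level and the null rate at which it was computed.
2. **Section 11.2.** State the same alpha and sidedness as the decision threshold for the primary test. Name one test, and define the primary comparison as classes A and B against the remaining classes, so that the stated power describes the planned analysis.
3. **If 95% at 0.012 is to be kept.** Plan for 21 per arm two-sided (20 falls just short at 94.98%) or 19 one-sided, plus an allowance for withdrawals. Two-sided, 2 × 21 = 42 exceeds the present ceiling of 40.

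Optionally, Boschloo's exact test on the same two-category table also controls type I error. It has 86.8% power at 0.012 and 96.5% at 0.05. The correction does not depend on it.

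Items 1 and 2 cost only wording and a less favourable stated power. They need no additional patients and no change to conduct.

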11.2. Planned Statistical Analysis

At the completion of the last study subject, the blinding will be broken and the aggregate results of the treatment and control arm will be compared.

The primary outcome measure is the change in monthly vertigo episodes. Per the AAO guidelines⁴, this has a numeric value of $X/Y \times 100$, where X is the average number of definitive spells per month after therapy, and Y is that rate prior to therapy. Categories A-F are designated, and the Chi-square/Fisher's Exact test will be used to compare the treatment and placebo groups.

[figure not shown]
Numeric Value	Class	Description
0	A	Complete control
1 to 40	B	Substantial control
41 to 80	C	Limited Control
81 to 120	D	Insignificant Control
> 120	E	Worsening of symptoms
	F	Secondary treatment initiated due to disability from vertigo

Secondary outcome measures are the average hearing threshold and word recognition score, which will be compared by repeated-measures ANOVA. Another secondary outcome measure is the patient Meniere's functional level before and after treatment (Appendix 2).

[figure not shown]

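### The stated 95% power does not belong to Fisher's exact test at 15 per arm and alpha 0.012 (82.8% two-sided, 86.8% one-sided), and section 11.2 leaves the primary test open; one test, level and sidedness should be fixed, and Boschloo's test is a cheap option

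*Combined protocol and SAP*

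**What the plan says.** Section 11.1 powers the trial on a binary outcome. It assumes that "the Mastoid Oscillation arm will have a 75% rate of achieving substantial or complete control" "and 12% for the placebo group". The design statement, for 15 subjects per arm, reads: "using Fisher's Exact test, the design has 95% statistical power with alpha of 0.012". It does not say whether the test is one- or two-sided, or whether 0.012 is the nominal level or an attained size.

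Section 11.2 describes the primary analysis differently. It defines six classes, A to F, offers chi-square as an alternative to Fisher, and says that the "Exact test will be used to compare the treatment and placebo groups". It gives no significance level, no sidedness, no rule for choosing between the two tests, and no split of the classes into responders and non-responders. Neither section mentions an unconditional exact test.

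Two other sections bear on the final arm sizes. Section 3.1 allows up to 40 enrolments to obtain 15 per arm. Section 6 withdraws subjects who miss visits and does not replace them.

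**The concern.** Fisher's test conditions on the total number of responders. With 15 per arm few p-values are attainable, so the test spends far less than its nominal error rate. A power figure computed by another route can therefore look right and still not belong to the test that will be run.

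The trial exists to answer the objection that the pilot lacked controls, and it has 30 subjects to do so. The only control rate in the plan (2 of 30, section 11.1) comes from a delayed-start group, not from a sham that reproduces the device's sound. If sham response is higher than 12%, power falls quickly and the choice of test matters more. If the choice between chi-square and Fisher is still open when the blind is broken, it could be made with the results in view.

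**Working it through.** **Inputs.** From section 11.1: n = 15 per arm, 75% versus 12%, alpha 0.012, Fisher's exact test, stated power 95%. Assumed because not stated: sidedness (both tried), nominal 0.05 as a comparison level, and placebo rates of 20% and 30% as sensitivity values.

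**Formulas.** Let b(k; p) = C(15,k) p^k (1−p)^(15−k).
- Power = Σ b(x; 0.75) b(y; 0.12) over all (x, y) that the test rejects.
- Maximum size = the largest value, over a common rate π, of Σ b(x; π) b(y; π) over the same tables.
- Boschloo's p-value for a table = the largest value, over π, of Σ b(x; π) b(y; π) over all tables whose Fisher p is no larger than the observed one.

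**Step 1: the plan's own figure.** For y placebo responders, two-sided Fisher at 0.012 needs at least c(y) treatment responders:

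| y | c(y) | b(y; 0.12) | P(X ≥ c(y)), rate 0.75 | product |
|---|---|---|---|---|
| 0 | 7 | 0.1470 | 0.9958 | 0.1464 |
| 1 | 9 | 0.3006 | 0.9434 | 0.2836 |
| 2 | 10 | 0.2870 | 0.8516 | 0.2444 |
| 3 | 11 | 0.1696 | 0.6865 | 0.1164 |
| 4 | 12 | 0.0694 | 0.4613 | 0.0320 |
| 5 | 13 | 0.0208 | 0.2361 | 0.0049 |
| 6 or more | 14 or 15 | | | 0.0004 |

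The products sum to 0.8281, so power is 82.8%. One-sided at 0.012 it is 86.8%. Neither is 95%; the shortfalls are 95 − 82.8 = 12.2 and 95 − 86.8 = 8.2 points.

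Other routes to the figure at 0.012, one-/two-sided:
- Pooled normal: 94.3% / 89.5%.
- Arcsine: 93.8% / 90.1%.
- Unpooled normal: 98.8% / 97.7%.

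The one-sided pooled normal and arcsine values come close to 95%, but they are not Fisher's test. Fisher at nominal 0.05 gives 92.0% two-sided and 96.5% one-sided, with maximum sizes 0.0177 and 0.0216, so 0.012 is not the attained size either. Two-sided Fisher at 0.012 gives 94.98% at 20 per arm.

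**Step 2: error rate used at 15/15 (two-sided).**

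| Nominal level | Fisher max size | Boschloo max size | Uncorrected chi-square max size |
|---|---|---|---|
| 0.05 | 0.0177 | 0.0433 | 0.055 |
| 0.012 | 0.0052 | 0.0091 | 0.016 |

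Fisher uses 0.0177/0.05 = 35% and 0.0052/0.012 = 43% of the nominal rate. Chi-square exceeds the nominal rate at both levels.

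**Step 3: power at 15/15, two-sided, 75% on treatment.**

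| Placebo rate | Level | Fisher | Boschloo |
|---|---|---|---|
| 2/30 (pilot control) | 0.05 | 97.4% | 99.0% |
| 12% (plan) | 0.05 | 92.0% | 96.5% |
| 12% (plan) | 0.012 | 82.8% | 86.8% |
| 20% (assumed) | 0.05 | 78.5% | 88.4% |
| 30% (assumed) | 0.05 | 55.6% | 70.4% |
| 30% (assumed) | 0.012 | 39.1% | 42.9% |

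At 15/15 Boschloo rejects every table that Fisher rejects, plus 20 more at 0.05 and 12 more at 0.012. For example, 8/15 versus 2/15 gives Fisher p = 0.0502 and Boschloo p = 0.0234.

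**Step 4: unequal or smaller arms (treatment/placebo), 75% versus 12%, two-sided.**

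| Arms | Fisher to Boschloo at 0.05 | Fisher to Boschloo at 0.012 |
|---|---|---|
| 14/15 | 93.7% to 95.9% (+2.2) | 85.9% to 86.8% (+0.9) |
| 15/14 | 93.0% to 95.6% (+2.6) | 84.4% to 85.7% (+1.3) |

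At 14/14 the gains are 4.2 and 6.9 points.

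**Step 5: the conditional cost.** For 4/15 versus 0/15, Fisher's two-sided p is 2 × C(15,4)/C(30,4) = 2 × 1365/27405 = 0.0996. Boschloo's is 0.043. At nominal 0.05 Boschloo rejects this table, so its error rate given exactly four responders in total is about 10%.

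**The case against.** Fisher's test is valid and standard, and choosing among valid exact tests is partly preference. That stands: nothing here shows an inflated error rate from Fisher's test.

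The conditional argument also stands. Patients come from one practice and are allocated from a predetermined 1:1 table. With group sizes fixed and under the sharp null, Fisher's p-value is the exact randomisation p-value. Boschloo controls error only on average over two independent binomials, and its extra rejections are tables whose Fisher p exceeds the level. A reader might infer that the two tests give the same type I guarantee; they do not.

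A reader might also take 15 and 15 as fixed. Sections 3.1 and 6 do not secure that. Equal small arms favour Boschloo's showing, and losing one subject from one arm roughly halves the gain at 0.05. At the pilot control rate the gain is 1.7 points, and the gain of about 15 points needs a 30% placebo rate that the plan does not assume.

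Finally, a reader might infer that Boschloo restores the promised 95%. It passes 95% at 15/15 only at two-sided 0.05, a level that the plan never states. At 0.012 it gives 86.8% two-sided (93.1% one-sided).

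The objection does not touch two defects: the quoted power is not that of the named test, and section 11.2 leaves open a test that exceeds its level.

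**Conclusion.** The point holds as a correction plus an efficiency option. The correction is firm: on the plan's own inputs, Fisher's test at alpha 0.012 has 82.8% power two-sided or 86.8% one-sided, not 95%, and the primary test, level, sidedness and dichotomy are not fixed in section 11.2. Conservatism explains only part of the gap, since replacing Fisher by Boschloo recovers 86.75 − 82.81 = 3.9 of the 12.2 points two-sided.

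The option is modest: 4.5 points at two-sided 0.05 on the planning rates at 15/15, less at a lower placebo rate or when one arm loses a subject, and more at 0.05 if sham response is higher.

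The figures assume two independent binomials on A or B versus C to F. They do not carry over to a six-class table. The documents do not support reading this as a type I error problem in Fisher's test. Nor do they show that the 95% was meant for 20 per arm, although twice 20 equals the enrolment ceiling.

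**What to change.** Before unblinding, amend sections 11.1 and 11.2 together:
- Define the primary comparison as class A or B versus C to F, which is the outcome that section 11.1 powers.
- Name one test, with its significance level and sidedness, and delete the open chi-square alternative.
- Restate the power for that test and level. If Fisher is kept, the two-sided figures are 82.8% at 0.012 or 92.0% at 0.05. If Boschloo is chosen, they are 86.8% or 96.5%. Add a row for unequal arms and one for a higher placebo rate.
- Preferably name Boschloo's unconditional exact test as primary and report Fisher's p-value alongside. State that its error control is unconditional, so the two p-values can fall on opposite sides of the level.

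The cost is a few sentences and one function call in standard software, with no added subjects. The downsides are a test less familiar to clinical readers and the loss of Fisher's conditional guarantee.
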